6. STUDY ASSESSMENTS

All study assessments will be performed as indicated in the schedule of assessments in [Table 8](#); the order of assessments is suggested by the order of mention within the schedule. Laboratory assessments are shown in [Table 9](#).

Table 8: Schedule of Assessments

Procedure	Section	Screening	Treatment				EOT	Follow-Up	Comments
		Day -28 to -1	Day 1	Day 8 (± 3 days)	Day 15 (± 3 days)	Day 28/Q28D (± 3 days)		EOT + 30-35 Days	
Informed consent	7.1	X							
Contact IVRS	7.2	X	X			X	X		
Inclusion and exclusion criteria	3.1 3.2	X	X						
Demography and medical history	7.3.1	X							
Prior/concomitant medications	7.3.2	X	X	X	X	X	X	X	
Physical exam/ weight/height	7.4.2 7.4.3	X*	X	X	X	X	X	X	*Comprehensive exam at screening; targeted physical exam thereafter. Height required at screening only.
Vital signs	7.4.4	X	X	X	X	X	X	X	
12-lead ECG	7.4.5	X*	X*	X**					*Triplicate ECGs will be performed during screening and on Day 1 before starting study treatment. **Triplicate ECGs will be performed predose and 2 hours (± 15 minutes) after receiving INCB039110 on Day 8. Additional ECGs may be performed as clinically indicated.
ECOG status	7.6.1	X	X			X	X	X	
AE assessment	7.4.1	X	X	X	X	X	X	X	
CT or MRI	7.5.1	X				X*	X		*Week 8, Week 16, and then every 16 weeks ± 1 week. Also required to confirm CR.
FDG-PET scan/PET-CT	7.5.2	X				X*			*Required at baseline and to confirm CR or if clinically indicated.

Table 8: Schedule of Assessments (Continued)

Procedure	Section	Screening	Treatment				EOT	Follow-Up	Comments
		Day -28 to -1	Day 1	Day 8 (± 3 days)	Day 15 (± 3 days)	Day 28/Q28D (± 3 days)		EOT + 30-35 Days	
Bone marrow exam	7.5.3	X*							*Required as a screening assessment unless performed as per standard of care within 60 days of Day 1. Repeat to confirm CR or if clinically indicated.
Dispense study drug	5.1		X			X			
Study drug accountability	5.4		X	X	X	X	X		
INCB039110 administration	5.2.1		X*	X*	X*	X*			*Subjects should refrain from taking INCB039110 on clinic visit days until after local laboratory blood samples are collected.
Ibrutinib administration	5.3.1		X*	X*	X*	X*			*Subjects should refrain from taking ibrutinib on clinic visit days until after local laboratory blood samples are collected.

FDG = fluorodeoxyglucose; PET = positron emission tomography.

Table 9: Laboratory Assessments

Laboratory Tests	Section	Screen	Day 1	Day 8 (± 3 days)	Day 15 (± 3 days)	Day 28/Q28D (± 3 days)	EOT	Follow-Up	Details
Local Laboratory Samples									

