7.5.1. Computed Tomography Scan or Magnetic Resonance Imaging

Subjects will undergo a diagnostic-quality CT or MRI to evaluate measurable disease during the screening phase. If CT/MRI assessment was performed as standard of care before signing of the ICF but within 28 days of Day 1, the results from that assessment may be recorded in the eCRF in lieu of a study-specific assessment.

On-treatment assessments should be repeated at Week 8, Week 16, and every 16 weeks thereafter.

This assessment schedule also applies to those subjects who discontinue study treatment for reasons other than disease progression until disease progression, start of new anticancer therapy, withdrawal of consent, end of the study, or death, whichever occurs first. Scheduled assessments should always be calculated from the first dose of study treatment. Imaging should not be delayed for delays in treatment.

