7.3. Analysis of the Primary Efficacy Parameter

7.3.1. Primary Efficacy Analysis

The primary variable for the Phase 2 of the study is ORR, which is defined as the proportion of subjects with best response (CR or PR) by modified Lugano Classification ([Cheson et al 2014](#)) for DLBCL. The proportion of responders within each treatment group will be estimated with 90% CIs by treatment group. Confidence intervals will be calculated based on the method of Koyama and Chen ([2008](#)) that accounts for early termination rules of the Simon 2-stage design. Within each treatment group, 1- sample binomial test will be used to test the null hypothesis.

In general, best response is determined on the subject level using the highest overall response achieved postbaseline. In the case of SD, measurements must meet the SD criteria at least once after study entry at a minimum interval of 56 days. Subjects who fail to meet these criteria will have best response of PD if the next available Lugano Classification evaluation after the initial scan indicates PD or NE if no additional evaluations are available.

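### The SAP's 56-day minimum for stable disease makes no allowance for the Week 8 scan window, so some on-schedule SD scans can be tabulated as PD or NE

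*SAP*

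**What the plan says.** SAP section 7.3.1 gives a general rule, that "best response is determined on the subject level using the highest overall response achieved postbaseline", and then a condition for stable disease: "In the case of SD, measurements must meet the SD criteria at least once after study entry at a minimum interval of 56 days". A subject who does not meet the condition is assigned "best response of PD if the next available Lugano Classification evaluation after the initial scan indicates PD or NE if no additional evaluations are available". The section does not mention a scan window, does not define study entry, and does not say whether the 56 days are elapsed days or study days.

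The CT/MRI comment in Protocol Table 8 reads "Week 8, Week 16, and then every 16 weeks ± 1 week". The on-treatment scans sit in the 28-day visit column, whose own window is ± 3 days. The same row also marks a scan at end of treatment (EOT).

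On the clock, Protocol section 7.5.1 says: "Scheduled assessments should always be calculated from the first dose of study treatment". It also continues the imaging schedule for subjects who stop treatment without progression. Protocol section 6.1 allows up to 2 days between enrollment and the start of treatment. SAP sections 4.1.1 and 4.1.2 set Day 1 as the date of first dose, with no Day 0.

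**The concern.** The SD threshold equals the nominal date of the first on-treatment scan (8 × 7 = 56), while the protocol lets that scan be done earlier. Take two subjects enrolled and first dosed on the same day, each with SD at the Week 8 scan and PD at Week 16. One is scanned on Study Day 54 and the other on Study Day 57. Both scans are compliant, yet the first subject's best response is PD and the second's is SD. The difference comes only from when the appointment was booked.

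The result appears in the best-response tables: 2.1.1.x for the safety run-in and ITT populations, and 2.1.2 for the per-protocol population. The next scheduled scan after Week 8 is at Week 16, and the synopsis expects about 4 months of treatment. SD followed by progression at the second scan is therefore a foreseeable course. At stake is whether these tables describe early progression and non-evaluability correctly.

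**Working it through.** **Inputs.** SD minimum: 56 days (SAP 7.3.1). First scan: Week 8, ± 7 or ± 3 days (Protocol Table 8). Lag from enrollment to first dose: 0 to 2 days (Protocol 6.1). Study day = date − Day 1 date + 1 (SAP 4.1.2).

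**Nominal day.** The coagulation row of Protocol Table 9 names Day 112 as a visit. Day 112 is 16 × 7, which points to Week 8 being Day 56. Counting 56 days on from Day 1 would give Day 57, so both are shown.

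**Formula.** Taking study entry as enrollment, elapsed days = study day − 1 + lag. A scan fails the rule if this is below 56.

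| Window | Week 8 is | Permitted study days | Elapsed days, lag 0 | Days failing, lag 0 | Elapsed days, lag 2 | Days failing, lag 2 |
|---|---|---|---|---|---|---|
| ± 7 | Day 56 | 49–63 | 48–62 | 8 of 15 | 50–64 | 6 of 15 |
| ± 7 | Day 57 | 50–64 | 49–63 | 7 of 15 | 51–65 | 5 of 15 |
| ± 3 | Day 56 | 53–59 | 52–58 | 4 of 7 | 54–60 | 2 of 7 |
| ± 3 | Day 57 | 54–60 | 53–59 | 3 of 7 | 55–61 | 1 of 7 |

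If the 56 is read as a study day instead, 7 or 6 of 15 days fail under ± 7, and 3 or 2 of 7 under ± 3. No combination gives zero. With Week 8 as Day 56, lag 0 and elapsed days, even a scan on the nominal day is one day short (56 − 1 = 55).

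**Later scans.** The earliest Week 16 scan is at 112 − 7 − 1 = 104 elapsed days, so SD at Week 16 always meets the rule.

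**What happens to an SD scan that is too early:**

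- Next evaluation is PD: best response is PD.
- No further evaluation of any kind: best response is NE.
- SD again at 56 days or more (EOT, follow-up or Week 16 scan): best response stays SD.
- Later CR or PR: the subject is a responder.

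**Decision rules.** ORR, the Stage 1 rule (10 or more of 22 to continue) and the success rule (29 or more of 60) count only CR and PR. Summing b(22, x, p) × P(Bin(38, p) ≥ 29 − x) over x = 10 to 22 gives 0.0949 at p = 40% and 0.800 at p = 55%, in line with the stated 1-sided 0.1 and 80%. SD, PD and NE are all non-response, so these figures do not depend on the SD rule.

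**The case against.** The strongest reply is that the rule needs more than an early scan to change a category. Table 8 schedules an EOT scan, and section 7.5.1 keeps imaging going after discontinuation without progression. A subject with SD on Day 50 who stops at Week 10 is due another scan, and SD on that scan meets the rule. NE arises only if those scans are missing as well. This stands and narrows the problem, but it does not help the subject whose next evaluation is PD.

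A second reply is that a minimum duration for SD is a conservative convention, and that Table 11 of the protocol sets none for 56 days to contradict. That is fair as far as the choice of length goes. The objection here is different: the length chosen makes the category depend on scheduling within a permitted window.

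Third, if study entry means enrollment, the clock can start up to 2 days before first dose, which makes 56 days easier to reach. This is correct and is reflected in the lag-2 columns, where some permitted days still fail.

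A reader might infer that every SD on an early-window scan is reported as PD or NE, or that 7 of 15 days means about 47% of SD subjects are misclassified. The documents support neither. Recoding also needs a next evaluation of PD or none, the fractions count calendar days, and no distribution of scan dates is given.

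**Conclusion.** The mismatch is real and is in the current text of both documents. Under either reading of the window, some protocol-compliant Week 8 scans showing SD fall short of the SAP minimum, by up to 8 elapsed days under ± 1 week (56 − 48) and up to 4 under ± 3 days (56 − 52). Such a subject is tabulated as PD or NE if the next evaluation is PD or absent.

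How many subjects this would affect cannot be derived. It depends on scan dates, on the course of disease and on whether EOT and follow-up scans are done.

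The effect is confined to the SD/PD/NE split in Tables 2.1.1.x and 2.1.2. It would be wrong to infer any effect on ORR, the Stage 1 rule or the 29-responder rule. Duration of response and durable response concern responders only, and PFS has its own dates and censoring table. The visible text defines no endpoint based on SD. The point is minor in severity, and worth making because the correction is almost free.

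**What to change.** In SAP section 7.3.1, replace the 56 days from study entry with the lower edge of the Week 8 scan window, counted from first dose on the SAP's own study-day scale. If ± 1 week applies and Week 8 is Day 56, the wording is Study Day 49 or later (56 − 7). Under ± 3 days it is Study Day 53 or later (56 − 3). The SAP should state which window and which nominal day it takes.

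The minimum should be written as a study day. A requirement of 49 elapsed days from first dose would still reject a scan on Study Day 49, which is 48 days after first dose.

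The cost is one line of the SAP and one programming constant, with no new data and no change to the scan schedule. The downside is that the SD category will accept slightly shorter disease control.

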7.4. Analysis of the Secondary Efficacy Parameter

7.4.1. Duration of Response

For objective responders, the DOR is the time from the first overall response contributing to an objective response (CR or PR) to the earlier of the subject's death and first overall response of PD (by Lugano Classification for DLBCL) occurring after the first overall response contributing to the objective response. Median DOR and 90% CIs will be estimated using the Kaplan-Meier method. Subjects who are still responding at the time of database freeze or discontinuation will be right-censored at the time of last valid radiologic assessment. The DOR evaluation will be performed separately for each treatment group, and no statistical comparison will be made.

7.4.2. Durable Response Rate

For objective responders, the durable response rate is defined as the percentage of subjects achieving a CR or PR (as determined by Lugano Classification) for ≥ 16 weeks since the time from the first overall response contributing to an objective response (CR or PR). Confidence intervals will be calculated based on the Clopper-Pearson method for binomial distributions.

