The study will lead to a decision between 2 prespecified hypotheses about the probability of an ORR, p . The null hypothesis H_0 : $p = 40\%$ reflects a response rate that would be of no clinical benefit, and the alternative hypothesis H_A : $p = 55\%$ is a response rate that might lead to larger, confirmatory studies. Using a Simon 2-stage optimal design, a total of 60 subjects will be needed for 80% power at 1-sided $\alpha = 0.1$ level. If there are 9 or fewer objective responders from the first 22 evaluable subjects, the null hypothesis will be considered as supported, and the study will be terminated. Otherwise, 38 additional subjects will be enrolled (Stage 2). Subjects who did not receive study treatment will be excluded from the analysis of Stage 1 and replaced.

Primary efficacy analysis: The study will be considered successful if the total number of objective responders is ≥ 29 in Phase 2. A 90% confidence interval will be calculated for the ORR.

Secondary efficacy [REDACTED] analysis: Median DOR and durable response rate (CR or PR ≥ 16 weeks) will be estimated with a 90% confidence interval. Median PFS will be estimated with 90% confidence intervals. [REDACTED]

Safety Analysis: Safety data will be tabulated with summary statistics.

TABLE OF CONTENTS

SYNOPSIS	3
LIST OF ABBREVIATIONS.....	16
1. INTRODUCTION	19
1.1. Overview of Diffuse Large B-Cell Lymphoma.....	19
1.1.1. Treatment for Advanced DLBCL	20
1.1.2. Treatment for Relapsed/Refractory DLBCL	21
1.2. Study Rationale.....	21
1.2.1. Inhibition of Janus Kinase as a Target for Cancer Therapy	21
1.2.2. Inhibition of JAK With INCB039110	23
1.2.3. Inhibition of Bruton's Tyrosine Kinase as a Target for Cancer Therapy.....	24
1.2.4. Combined Inhibition of JAK and BTK in DLBCL	25
1.3. Potential Risks and Benefits of the Treatment Regimen	26
1.3.1. INCB039110.....	26
1.3.2. Ibrutinib	27
1.3.2.1. Summary of Clinical Safety.....	27
1.3.2.2. Risks	28
1.3.2.3. Cytopenias	28
1.3.2.4. Atrial Fibrillation.....	28
1.3.2.5. Second Primary Malignancies	28
1.3.2.6. Tumor Lysis Syndrome	28
1.3.2.7. Diarrhea	29
1.3.2.8. Rash	29
1.3.2.9. Interstitial Lung Disease	29
1.3.3. Potential Risks and Benefits for the Combination of INCB039110 and Ibrutinib	29
2. STUDY OBJECTIVES AND ENDPOINTS.....	30
2.1. Study Objectives.....	30
2.1.1. Phase 1	30
2.1.1.1. Primary Objective.....	30
2.1.1.2. Secondary Objective.....	30
██████████	30
2.1.2. Phase 2.....	30

2.1.2.1.	Primary Objective.....	30

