9.4.2. Secondary Analyses

The DOR is defined as the difference of the end of response and the start of response for subjects who have achieved a response. The start of a response will be the first visit where the subject achieves PR or better based on the Lugano Classification.

Duration of response will be assessed using Kaplan-Meier method for subjects who achieve a response. Median duration and 90% CI will be estimated. Subjects who are still responding at the time of database freeze or discontinuation will be censored at the last valid radiologic assessment visit.

The durable response rate is defined as CR or PR for ≥ 16 weeks as determined by Lugano Classification. The rate of responders will be estimated together with 90% CI.

Progression-free survival (PFS) will be determined from the enrollment date until the earliest date of disease progression, as measured by investigator assessment of objective radiographic disease assessments per Lugano Classification, or death due to any cause if earlier.

Progression-free survival data will be analyzed using Kaplan-Meier method, treating subjects with no observed death or progression as censored at the last valid radiologic assessment visit. Median PFS and 90% CI will be estimated.

All the efficacy endpoints (ORR, DOR, and PFS) of subjects from the safety run-in population will be summarized separately as appropriate with data availability.

Subgroup analyses for the subtypes will be explored, including but not limited to response by IPI as well as other disease characteristics.

[REDACTED]

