2.3.2.2. Secondary Endpoints

- DOR, defined as the time from earliest date of disease response until earliest date of disease progression.
- Durable response rate, defined as the percentage of subjects achieving a CR or PR for > 16 weeks.
- PFS, defined as the time from enrollment until the earliest date of disease progression determined by objective radiographic disease assessments, or death due to any cause.
- OS, defined as the date of enrollment until death due to any cause.
- Safety and tolerability via assessment of the frequency, duration, and severity of AEs and SAEs, and changes in clinical and laboratory assessments.

[REDACTED]

- [REDACTED]
- [REDACTED]

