5. STATISTICAL METHODOLOGY

5.1. General Methodology

Unless otherwise noted, SAS[®] software (SAS Institute Inc, Cary, NC; version 9.1 or later) will be used for the generation of all tables, graphs, and statistical analyses. Descriptive summaries for continuous variables will include, but not be limited to, the number of observations, mean, standard deviation, median, minimum, and maximum. Descriptive summaries for categorical variables will include the number and percentage of subjects in each category.

For the Phase 1 portion of the study, the safety run-in population (defined in Section 5.3.3) will be used for all safety analyses. For the Phase 2 portion of the study, the safety evaluable population will be used for all safety analyses, and the ITT population will be used for all efficacy analyses. [REDACTED]

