5.3. Analysis Populations

5.3.1. Intent-to-Treat Population

The ITT population will include all subjects enrolled into the Phase 2 portion of the study. This population will be used for analyses of all efficacy data.

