10.1. Changes to Protocol-Defined Analyses

Not applicable.

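### The durable response rate has two thresholds, an unsettled denominator and no valid way to score responders censored before 16 weeks

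*SAP*

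**What the plan says.** **Declared endpoint.** SAP 2.3.2.2 has "Durable response rate, defined as the percentage of subjects achieving a CR or PR for > 16 weeks". Protocol 2.2.2.2 and the synopsis endpoint list say the same.

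**Analysis text.** Protocol 9.4.2: "The durable response rate is defined as CR or PR for ≥ 16 weeks as determined by Lugano Classification". The synopsis statistical methods: "Median DOR and durable response rate (CR or PR ≥ 16 weeks) will be estimated with a 90% confidence interval". SAP 7.4.2 begins "For objective responders, the durable response rate is defined as the percentage of subjects achieving a CR or PR", sets the limit at 16 weeks or more from first response, and plans a Clopper-Pearson interval without a level. The Protocol supplies the 90%.

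**Population.** SAP 5.1 states that "the ITT population will be used for all efficacy analyses", and SAP 5.3.1 says of the ITT population: "This population will be used for analyses of all efficacy data". Appendix B labels the durable response table (2.4.2) ITT. It gives the DOR table (2.4.1) the same label. SAP 10.1, headed "Changes to Protocol-Defined Analyses", records none.

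**Follow-up.** Protocol 9.4.2: "The DOR is defined as the difference of the end of response and the start of response for subjects who have achieved a response". SAP 7.4.1 censors continuing responders at the last valid scan, at database freeze or discontinuation. Imaging is at Weeks 8 and 16 and every 16 weeks after that, ±1 week (Protocol Table 8). Protocol 4.5 ties database lock to the last subject being evaluable for response, a term it does not define.

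**The concern.** Two analysts who both follow the plan could report different percentages under one endpoint name. They could differ on three things:

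- the operator, more than 16 weeks or 16 weeks and over;
- the denominator, all subjects or responders only;
- the status of a responder whose follow-up ends before 16 weeks.

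The third does not depend on how any sentence is read. A binomial proportion needs a yes or no for every subject, and a responder censored at, say, 56 days is neither. The SAP has censoring rules for DOR, PFS and OS, but none for this endpoint. In an open-label, single-arm study these choices should not be left until the data have been seen.

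**Working it through.** **The plan's own figure.** No size or power is stated for the durable response rate. The nearby design figure reproduces exactly. Continuing on 10 or more of 22 and succeeding on 29 or more of 60 gives one-sided alpha 0.0949 at p = 0.40 and power 0.8004 at p = 0.55. Nothing below changes that.

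**1. Operator and scan windows.** Inputs: scans at Weeks 8, 16, 32, 48 and so on, each ±7 days (Protocol Table 8). The gap between two scans is the nominal gap ±14 days.

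| First response → later scan | Nominal days | Range |
|---|---|---|
| Week 8 → 16 | 56 | 42–70 |
| Week 8 → 32 | 168 | 154–182 |
| Week 16 → 32, and every later single gap | 112 | 98–126 |

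A subject who first responds at Week 16 and progresses at Week 32, both on schedule, has exactly 112 days. That is durable under one operator and not under the other. If actual dates are used and each scan day is independent and uniform over its 15 possible days (assumed), the two offsets cancel with probability 1/15 = 6.7%. The gap is below 112 days with probability (1 − 1/15)/2 = 46.7%. Scan-day variation would then decide the classification.

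**2. Denominator.** The responder-only rate equals the all-subjects rate times N/responders:

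- 60/24 = 2.50 at the null rate of 40%;
- 60/29 = 2.07 at the success boundary;
- 60/33 = 1.82 at the alternative of 55%.

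With 29 responders and 15 durable (assumed counts), the 90% Clopper-Pearson results are:

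- 15/60 = 25.0% (16.1 to 35.9);
- 15/29 = 51.7% (35.2 to 68.0).

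**3. Early censoring.** From the table, a Week 8 responder still responding at Week 16 has at most 70 days observed. A Week 16 responder has none until the next scan. So no continuing responder can show 112 days on scheduled scans before Week 32. Each unclassified responder moves the all-subjects rate by 1/60 = 1.7 points. With 15 shown durable and 4 censored early (assumed), the rate is 15/60 = 25.0% if the 4 count as non-durable. It is 19/60 = 31.7% (21.8 to 42.9) if they count as durable.

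**4. Direction and possible size of the bias.** This is a simulation in which only n = 60 and the scan weeks come from the documents. Assumed inputs:

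- uniform accrual over 12, 18 or 24 months;
- ORR 0.55, with first response at Week 8 in 50% or 75% and otherwise at Week 16;
- exponential DOR with median 16, 26 or 40 weeks;
- no discontinuation;
- lock 7 days after the last subject's nominal Week 8, 16 or 32.

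Entries are ratios to the rate with full follow-up.

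| Lock at last subject's | Raw, censored = non-durable | Kaplan-Meier × ORR |
|---|---|---|
| Week 8 | 0.48–0.75 | 0.85–0.96 |
| Week 16 | 0.63–0.83 | 0.92–0.99 |
| Week 32 | 0.94–0.98 | 0.98–1.00 |

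The Kaplan-Meier ranges also span runs with 3% discontinuation per 28 days. I checked the no-discontinuation pattern independently and it agrees closely. In a subset of the simulated settings, the Clopper-Pearson 90% interval on the raw proportion covered the full-follow-up rate in 1.2% to 64.0% of runs. The bootstrap interval for Kaplan-Meier × ORR covered it in 74.8% to 92.8%.

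**5. Consistency of the alternative.** With no early censoring, the Kaplan-Meier rate is durable/responders. Multiplied by responders/N it gives durable/N, the raw proportion. The two estimates part only when someone is censored early.

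**The case against.** **The denominator is nearly settled.** ITT is assigned to all efficacy data and to Table 2.4.2, and SAP 7.4.2 itself speaks of a percentage of subjects. That stands as evidence of intent, and the roughly twofold figures measure the less likely reading. It is not conclusive: the DOR table is also labelled ITT, although DOR exists only in responders, and SAP 7.4.1 opens with the same restriction and means it. A reader might infer that the SAP has changed the endpoint to a responder rate without declaring it. The documents do not support that; the wording is ambiguous.

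**The censoring rule may be implicit.** To achieve a response of 16 weeks could mean to be shown to achieve it, so that early-censored responders count as non-durable. That reading is possible. But it is not written down, and it yields a lower bound rather than an estimate of the rate. A reader might equally infer that the plan will report a rate biased downward. The plan neither states nor excludes that scoring.

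**Discontinuation may cause little censoring.** Protocol 7.5.1 continues the imaging schedule after treatment stops for reasons other than progression, and SAP 7.4.1 does not say whether it means discontinuation of treatment or of study. This stands, so the case here rests on lock timing and not on a discontinuation rate.

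**The endpoint is secondary, with no test or decision rule.** True, and it limits the weight of the point.

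**Conclusion.** The point holds as one of inconsistent definition and an unsuitable estimator.

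- **Threshold.** It contradicts itself within the Protocol and within the SAP, at a value the scan schedule is built to produce.
- **Denominator.** It is ambiguous, with all subjects the likelier intent. The responder reading would multiply the rate by 1.82 to 2.50 for 33 down to 24 responders of 60.
- **Early-censored responders.** A plain proportion has no valid way to score them. Counting them as non-durable biases the rate downward. The size depends on accrual, DOR and lock timing, which the documents do not give, so the simulated ratios show direction and plausible scale only.

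The missing interval level in SAP 7.4.2 is minor, since the Protocol gives 90%. The primary ORR rule and both Simon decisions are unaffected. The plan should be corrected, but no go or no-go decision turns on it.

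**What to change.** 1. **Denominator.** In SAP 7.4.2 delete the opening restriction to responders and name the denominator used for ORR. Reconcile it first: ITT is all enrolled Phase 2 subjects (Protocol 9.1, SAP 5.3.1), but the synopsis, Protocol 4.1.2 and SAP 3.1.2 exclude enrolled-but-untreated subjects from the efficacy analysis. Label any responder-only percentage as such.
2. **Threshold.** Use one operator in all six places: the synopsis endpoints, the synopsis statistical methods, Protocol 2.2.2.2 and 9.4.2, and SAP 2.3.2.2 and 7.4.2. Add a window convention, for example counting in nominal scan weeks, so that every nominal 16-week gap is classified alike.
3. **Estimator.** Suggested text:

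> If any responder is censored before 16 weeks, the main estimates are the 16-week Kaplan-Meier rate of DOR with a 90% CI, and that rate multiplied by the ORR with a 90% bootstrap CI (resampling subjects). The observed proportion is shown only as a lower bound, with the number of responders censored early. Its Clopper-Pearson interval is not presented as a 90% CI for the durable response rate. If none is censored early, the observed proportion is reported with a 90% Clopper-Pearson CI.

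   Read the Kaplan-Meier curve just before 16 weeks if the operator is 16 weeks or more, and at 16 weeks if it is more than 16.
4. **End of response.** Use one event definition for DOR and durability. The endpoint lists in both documents name progression only; SAP 7.4.1 takes the earlier of death and PD.

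**Cost.** A short wording amendment and one extra analysis from DOR data already planned (SAP 7.4.1, Listing 2.6.4). No later data cut is needed. The Protocol edits need sponsor and IRB/IEC approval (Protocol 10.1). The bootstrap interval may under-cover when follow-up is very short, at about 75% to 78% in the least favourable simulated case (12 months' accrual, Week 8 lock).
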